### **Objective II:**

Objective II is to test the hypothesis that actual and imagined movements and movement disorders are the result of ongoing and movement related activity of single neurons, local field potentials and EEG activity recorded from cortical structures and deep nuclei (basal ganglia and thalamus).

Date: February 19, 2023

Principal Investigator: [name].

Application Number: NA\_00079932

The primary outcome is to establish the effect of ongoing and evoked spike, local field potential and EEG activity recorded from cortical and deep nuclei upon movement disorders such as tremor, Parkinson's disease, dystonia and dyskinesia. Analysis of these results for functional connectivity will allow us to characterize networks involved in movement disorders.

Secondary outcomes will include determination of the influence of actual and imagined movements upon ongoing and movement related spike, local field potential, and EEG activity recorded from cortical and deep nuclei.

We also will investigate the effects of direct cortical stimulation with electrical pulses on the motor cortex and other cortices by measuring electrophysiological signals, and will evaluate stimulation effects on disease symptoms.

Additionally, we will determine whether scalp-applied tDCS over the motor cortex also results in modulating single neuron spiking activities or changes in cortical phase –amplitude coupling.. This will be helpful in providing more understanding of the mechanisms of action of DBS and tDCS, and may indicate the usefulness of integrating the two different types of brain stimulation in the future.

Other secondary outcomes will determine whether motor learning or adaptation are the result of ongoing and movement related spike, local field potential and EEG activity recorded from cortical and deep nuclei.

Other secondary outcomes will also include the determination of the mechanisms of speech characteristics as coded in the basal ganglia-thalamocortical network during production and auditory processing of speech based on specific task related spike, local field potential, and EEG activity recorded from cortical and deep nuclei.

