An approach that has been attempted recently for PD symptom control is transcranial direct current stimulation (tDCS). tDCS is a non-invasive procedure in which direct current (typically 1-2mA) is passed through anode and cathode electrodes that are placed on the head and localized using MRI, transcranial magnetic stimulation (TMS), or EEG. tDCS was first used by Fregni et al. on PD patients. They examined patients in the moderate stage who were off medication for 12 hours and found that application of anodal tDCS over the left primary motor cortex (M1) produced 20% improvement of clinical motor scores (as compared to sham stimulation). In this proposal, we will investigate the effects of tDCS on neuronal activity of the deep nuclear structures and also changes in phase –amplitude coupling at the cortical level (de Hemptinne et al., 2015) to seek possible explanations for the mechanism of action of DC stimulation.

Tonic pulsed motor cortex stimulation was introduced in early 1990 for the relief of chronic facial pain (Tsubokawa et al., 1991a, b) and recently, its use has been extended to exploration in patients with movement disorders. There is some evidence that direct cortical stimulation of the motor cortex through strip electrode contacts may relieve the motor symptoms of patients with PD (Canavero et al., 2002, 2003; Pagni et al., 2005, 2005). It may also provide some benefit for patients with PD during concurrent STN-DBS after chronic implantation and in long-term follow-up (Cioni, 2007, Meglio and Cioni, 2009). Motor cortex stimulation is highly influenced by DBS technology and in some studies uses a similar pulse generator. The stimulation pulse trains are similar to DBS systems, with similar adjustable parameters (Canavero et al. 2002, 2003; Cilia et al. 2007, 2008; Fasano et al. 2008; Gutierrez et al. 2009; Pagni et al. 2005; Strafella et al. 2007; Tani et al. 2007).

In order to investigate the neurophysiological role of the basal ganglia in speech production and control, subjects will perform speech production tasks intraoperatively. For each recording site, this will generate the data needed to characterize the scale and level of encoding and gain effects within single neurons, their surrounding local field potential (LFP), and their synchrony with sensorimotor cortex electrocorticography (ECoG).

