9) **Direct Cortical Stimulation:** The contacts from the subdural strip electrode, which is placed on the hand motor area, are utilized in either a unipolar or a bipolar configuration to deliver the stimulation current. The stimulation parameters will roughly fall into the ranges (amplitudes from 2 mAmp to 6 mAmp, rates from 10 Hz to 130 Hz, and pulse widths from 60  $\mu$ sec to 450  $\mu$ sec) (Canavero et al., 2003; Canavero et al., 2002; Cilia et al., 2007; Cilia et al., 2008; Fasano et al., 2008; Gutierrez et al., 2009; Pagni et al., 2005; Strafella et al., 2007; Tani et al., 2007). Direct cortical stimulation will be delivered by either the Alpha Omega NeuroOmega data acquisition system (Nazareth, Israel), or the Blackrock Microsystems NeuroPort data acquisition system incorporating the CereStim applicance (Salt Lake City, UT).

Date: February 19, 2023

Principal Investigator: [name].

Application Number: NA\_00079932

10) **Auditory Stimulation and Speech Testing:** A conventional speaker including earphones will be used to produce auditory stimulation and a high quality microphone will be used to record the sound of the subjects in the speech production task. In some tasks, participants will repeatedly read aloud syllable triplets, in which each triplet will be composed of items drawn from a pool of 16 syllables. The subject's voice may be recorded, and also played back to them using an earphone. Stimuli: The "basis set" for many experiments will be 4 consonants and 4 vowel phonemes, chosen such that they comprise different combinations of 5 articulator features, and 8 major phonetic state spaces (4 C and 4 V; lower portion of grid) described in human motor cortex. These will be combined to create 16 unique CV syllables, which vary in the frequency of occurrence and lexical status. The composition of this stimulus set will allow us to probe for multiple levels of encoding in the context of a single speech production task and acquired datasets. Other stimuli will also be used consisting of speech segments and tone sequences with similar outcome measures of correlation with the neural recordings.

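### The speech tests correlate sound-related events with neural recordings made during sound, but no step checks whether the sound itself has entered those recordings

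*Combined protocol and SAP*

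**What the plan says.** Section 2 (Objective II) lists among the secondary outcomes the "determination of the mechanisms of speech characteristics as coded in the basal ganglia-thalamocortical network", during both production and hearing of speech. Section 3 (Objective II: Motor Control) states that "subjects will perform speech production tasks intraoperatively" and that the data from each recording site should "characterize the scale and level of encoding and gain effects within single neurons", in the surrounding LFP, and in synchrony with ECoG.

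Section 4, item 10 (Auditory Stimulation and Speech Testing) describes the sound sources. A speaker or earphones deliver stimuli and a microphone records the patient. The patient's voice may be recorded and "also played back to them using an earphone". The main task is reading aloud triplets drawn from 16 syllables. For the remaining material the plan says: "Other stimuli will also be used consisting of speech segments and tone sequences with similar outcome measures of correlation with the neural recordings". The word *similar* implies that the syllable task uses the same kind of measure.

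Section 7 (Study Statistics) offers a correlation or concordance correlation coefficient for any pair of outcomes. Its lists of outcome variables do not mention speech.

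**The concern.** A correlation between sound and a neural channel has two possible sources: neurons that respond to or drive the sound, or the sound reaching the electrode, leads or amplifier by mechanical vibration or electrical coupling. Pickup is a copy of the audio, so it correlates with the audio whether or not any neuron is involved. Both routes are plausible here, because the patient speaks with electrodes in place and an earphone may be driven during recording.

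The bias would be systematic. More trials would make a contaminated channel look more convincing, not less. Without a check, a positive encoding result in LFP or ECoG could not be told apart from a recording artefact.

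**Working it through.** **Step 1. Is there a safeguard anywhere?** The plan states no sample size, alpha, power or correlation threshold for this outcome, so there is no figure to reproduce. The nearest passages are:

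- Section 6, Auditory Equipment Description: a shielded cable, chosen to improve the speech recording. It does not concern the neural channels.
- Section 6, Respiratory Effort Sensor: resistance to artefact, but only of the breathing belt.
- Section 8, Auditory Stimulation and Speech Recording: played sound is kept under 60 dB, for the sake of the ears. This does not cover the patient's own voice.
- Section 7: a generic correlation coefficient, with no artefact rule or null distribution.

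None screens neural channels for audio.

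**Step 2. What would pickup do to a waveform correlation?** Assume channel = s + g·a, where s is neural activity independent of the audio a, and both have unit variance. Then

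r = g / √(1 + g²), and pickup's share of variance is p = g² / (1 + g²), so r = √p.

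- p = 1%: r = √0.01 = 0.10
- p = 10%: r = √0.10 = 0.32

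**Step 3. How often would a non-encoding channel be called significant?** Assume a two-sided test at 0.05 with the Fisher z approximation: probability = Φ(atanh(r)·√(n−3) − 1.96) + Φ(−atanh(r)·√(n−3) − 1.96), where n is the effective number of independent samples. Leakage is relative to the neural signal, g = 10^(dB/20). Leakage, n and alpha are all assumptions.

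| Leakage | r | n = 200 | n = 1000 | n = 5000 | n = 20000 |
|---|---|---|---|---|---|
| −40 dB | 0.010 | 5% | 6% | 11% | 29% |
| −30 dB | 0.032 | 7% | 17% | 61% | 99% |
| −20 dB | 0.100 | 29% | 88% | 100% | 100% |
| −10 dB | 0.302 | 99% | 100% | 100% | 100% |

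Example: at −20 dB and n = 1000, atanh(0.0995)·√997 = 3.15; 3.15 − 1.96 = 1.19; Φ(1.19) = 0.88. Simulation with 4,000 replicates at n = 1000 gave 5.1% with no leakage, then 16.7%, 88.3% and 100% at −30, −20 and −10 dB.

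So modest leakage is enough to mislead, while very small leakage matters only with many effective samples.

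**Step 4. Which measures are exposed?** The algebra applies to waveform-level correlation in the audio band. Power in a contaminated band would also follow loudness, though not by this formula. Syllable-label analyses are exposed less directly, because acoustic content differs between syllables. Sorted spike rates are exposed least.

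**Step 5. Properties of a simple screen.** A cut at the 95th percentile of a shuffled null flags 5% of clean channel-bands by construction. With ten independent bands, 1 − 0.95¹⁰ = 40% of clean channels would fail at least once. If identical tones repeat at fixed phase, shuffling audio across trials leaves the coherence intact and the screen would miss pickup. A true neural response phase-locked to heard sound would also be flagged. The fix has to deal with all three.

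**The case against.** The strongest reply has four parts.

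First, the plan never says that the audio waveform is the variable correlated. The syllable set is built from articulatory and phonetic features, which suggests label-type predictors, and single neurons are named before LFP and ECoG. This stands: it narrows the exposure and confines √p to an illustration. It does not remove the gap, because LFP and ECoG synchrony are also named as carriers of encoding.

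Second, neither pickup nor its size is documented. This also stands, and the conclusion is conditional on it.

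Third, this is an umbrella application for an exploratory study. It gives little preprocessing detail for any recording, and the speech work also runs under a separately funded project with its own ethics approval elsewhere (Data Sharing). A check may exist there. But the plan at hand neither states nor points to one, and exploratory status does not cure a bias that grows more convincing with more data.

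Fourth, the audio is kept, so the check can be run at any time. That is true, and it makes the fix cheap. It is still better fixed before encoding results are seen.

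Two stronger readings are tempting. Because Section 3 lists soft voice and monopitch as features of Parkinson's disease, a reader might infer that pickup would create a false disease-related gain effect. The documents do not support this. No intraoperative speech contrast between disease groups is described, healthy controls are studied only outside the operating room, and monitoring there is EEG alone (Timeline/Timing of Procedures). A reader might also infer that contaminated data will be pooled with the second centre. Data Sharing states that data are shared through a common database; it does not state a pooled analysis.

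**Conclusion.** The concern holds in conditional form. The plan judges the speech and auditory tests by correlation with recordings made during sound and reads the result as encoding, without any step that could separate coding from pickup. If pickup is present, LFP and ECoG measures sharing the audio band would show spurious encoding.

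The size cannot be fixed from the documents. Under the assumptions above, a non-encoding channel with leakage 20 dB below the neural signal would be called significant about 29% of the time at an effective n of 200 and 88% at 1000, against a nominal 5%; at −40 dB the figures are 5% and 6%. These apply to waveform correlation only.

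The outcome is secondary and the study exploratory, so the change is advisable but does not bear on the study's other outcomes.

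**What to change.** Add the following to Section 7 for the speech and auditory tests:

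1. For each channel and session, compute coherence between the recorded microphone or stimulus signal and the neural signal in the voice or tone band.
2. Compare it with a surrogate null: audio shuffled across trials, or randomly time-shifted audio where identical tones repeat. Control multiplicity across channels and bands.
3. Flag channel-bands above the threshold rather than deleting them automatically. For heard sounds, examine latency before excluding any: zero lag suggests pickup, a delay suggests a neural response.
4. Report encoding results with and without flagged channel-bands. Base encoding claims on findings that survive without them, or on measures outside the audio band: sorted spike rates, or power envelopes from bands below the voice range. Envelopes from within the voice range are not safe, since contaminated power still follows loudness.

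The cost is modest extra analysis. The audio is already recorded, so there is no new procedure and no added burden for the patient. The downside is that some channel-bands carry less weight, possibly including a few that are clean or truly phase-locked.

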### Objective III: Sensory Processes: Behavioral Tasks

These tasks will include attention tasks and a learning task which involves the painful and nonpainful stimuli, as described above under *Sensory Processes: Sensory stimulation*, including Heat Stimuli (Laser -2 and Thermode-3), and Electrical Stimuli-7. Attentional protocols will be carried out in one session, often with presentation of a painful (laser, thermode, or electrical), and a nonpainful (electrical or thermode) stimulus presented in a single train in random order. The subject is instructed to either: i) count or ii) push buttons in response to the painful stimulus (attention to pain), or the non-painful stimulus (distraction from pain) or both, as presented in random order and counterbalanced across patients. In three other tasks, a single train will consist of: i) only nonpainful stimuli which the patient counts, ii) only painful stimuli which the patient counts and iii) only painful stimuli while the patient performs a cognitive task, e.g. reading for comprehension.

Some subjects in both categories will be involved in protocols for classical conditioning or learning, which occurs when a neutral conditioned stimulus (CS+, a light or sound) is paired with an unconditioned aversive or appetitive (reward) stimulus (US). In the case of aversive conditioning, the US might be the painful cutaneous laser, thermode, or electrical stimulus, while in appetitive conditioning it might be a reward of one dollar. As measures of psychological variables, we propose to administer psychological questionnaires including depression, anxiety and PTSD scales.

Under Objective I extra-operative studies will often be carried out over a two hour session during which painful and nonpainful stimuli will be presented in a single train. During the extra-operative conditioning protocol, two or three sessions may be carried out on different days. Within each session there will be rest periods and between two and six separate trials with either attentional or conditioning tasks. The length of the intraoperative sessions will be less than one hour in length.

In this protocol the conditioning phase (one session) will be followed by the extinction phase (one session) during which the CS will be presented repeatedly without the US. Thereafter, the reversal of extinction phase will occur (one session) in which the return of the CR will occur spontaneously, or by reinstatement or by renewal. As a measure of autonomic activation we will record the skin conductance throughout all phases of conditioning by use of a Skin Conductance Coupler (V71-23, Colbourn Instruments, Boston MA).

In summary, under this cognitive protocol separate trials will include sessions of the habituation phase which is involves unpaired presentation of stimuli, the acquisition phase which involves the

Date: February 19, 2023

Principal Investigator: [name].

Application Number: NA\_00079932

paired presentation of stimuli, and extinction of conditioning and reversal of extinction phases. Decreased extinction or increased reversal of extinction may characterize pathologic fear or anxiety traits. Each of these phases may comprise a separate session or trial of the conditioning protocol as described above. Intraoperative studies will involve only attention testing or the conditioning and extinction phases of conditioning protocols.

Some healthy subjects, chronic pain patients, and the patients described above with epilepsy will be involved in attentional and learning protocols as described above. Stimuli are listed above (Objective II: Sensory Processes: Sensory Stimulation) and include laser (item 2), Thermode (item 3) and electric (item 7) in a single train, or two levels of stimulus intensity of one modality in a single train, e.g. low and high levels of the electric modality. Either modality may be nonpainful, or painful with a pain level of less than 6 out of 10 on a scale in which 0 is no pain and 10 is the worst pain imaginable. Often one of the two modalities of stimulation will often be painful while the other is nonpainful. The two modalities or intensities of stimuli will be applied at random interstimulus intervals and in random order, so that one stimulus may be less frequent (e.g. 5 to 25% of total stimuli) than the other (e.g. 95 to 75%). The subject will be asked to count the stimuli or signal the occurrence of one or both stimuli by key presses, which indicate detection of that stimulus.

Prior to using the laser in any participant, a calibration and verification procedure will be followed. Specifically both beam diameter and energy output will be measured.

“1. Energy output

a. Measure energy with thermopile and energy meter. The routine will be a series of energies such that the settings are 11 J, 12 J, 13 J, 14 J, 13 J, 12 J, 11 J, 12 J, 13 J, 14 J, 13 J, 12 J, 11 J, 12 J, 13 J, 14 J, 13 J, 12 J, 11 J. This series of up-and-down continuous staircase covers the range of stimuli used in our protocol and accounts for laser energy output hysteresis.

b. Save the results. Make sure the average of each energy output as measured is no more than 10% more than the expected value.

c. Record the results in participant binder.

2. Beam diameter

a. Save and date back of zap-it paper. Measure beam diameter at 11 J, 12 J, 13 J, and 14 J on zap-it paper to ensure the 10 mm diameter setting. Measure each energy output measure three times with Zap-it Grid paper. Confirm that the maximum spot on the zap it paper is not more than 10.9 mm, while the smallest spot is no less than 9.1 mm. Record the results in participant binder.”

Extraoperative studies will be carried out in healthy subjects and the patient population described above. Sessions of attention will involve one session while those of conditioning will involve two or three sessions. The intra-operative studies will be carried out over multiple sessions, each session for recordings from a single neuron. In many of these sessions painful (laser) or nonpainful (electric) somatic stimuli, and other stimuli will be presented in a single train. The length of the combined sessions will be less than one hour in total.

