Activation by sensory stimuli or movements will be determined by examining changes in neuronal firing rates, ongoing EEG frequency and spectral power as recorded from the structures named above. Cortical or deep structures jointly processing sensory signals will be identified by calculation of correlation, coherence and causality between the EEGs or LFPs recorded from these structures in response to sensory stimuli. Coherence is a measure of synchrony (and functional connections) between signals from different electrodes, and causality is a measure of the extent to which signals at one electrode are causal of those at another electrode (Glaser and Ruchkin, 1976; Granger, 1969; Liu et al., 2011c). All regulatory aspects of this study will be the responsibility of the study coordinator ([name]) and the PI.

Transcranial direct current stimulation (tDCS) is a commonly used non-invasive form of brain stimulation for studying motor functions in health and disease. It involves the attachment of surface electrodes to the scalp through which very small electric currents (1 or 2mA) are applied via a current regulated device that is powered by a battery. The currents do not produce any sensation. Importantly, when the electrode is placed over the region of the motor cortex, the small currents appear to affect the excitability of the neural tissue, as measured by the size of the motor evoked potential (MEP) induced by a single pulse of transcranial magnetic stimulation and recorded in hand muscles. tDCS will be used intraoperatively to demonstrate the functional connectivity between primary motor cortex and the subthalamic nucleus. We wish to characterize the mechanisms of action of tDCS as a noninvasive cortical stimulation for motor symptom control in PD patients (Benninger et al., 2010).

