### **Surgical Standard of Care Procedures:**

The target for the procedure is first estimated radiologically and then confirmed by recording physiological signals in the brain. As a part of the radiologic localization, the stereotactic frame is applied and the location of the lesion or implant site for the stimulator is determined by imaging in either the magnetic resonance imaging (MRI) or the computerized tomography (CT) suite.

Physiological confirmation of the optimal target site is determined during the procedure in the operating room. Placement of the electrode in the brain is carried out through a scalp incision and a dime sized hole in the skull. The radiologic prediction of the target is then confirmed using Standard physiological recording includes recordings of electroencephalography (EEG), field potentials and neuronal action potentials, as well as electromyography (EMG), and accelerometry. The surgical procedures target the Ventral intermediate nucleus of the Thalamus (Vim), the Subthalamic nucleus, and the Globus Pallidus in patients being treated for tremor, Parkinson's disease, and dystonia, respectively.

The procedure is completed by implanting a stimulator at the target which has been estimated radiologically and confirmed electrophysiologically. The standard physiological procedure involves

Date: February 19, 2023

Principal Investigator: [name].

Application Number: NA\_00079932

different maneuvers to characterize the neuronal activity including: a detailed sensory examination, performance of different voluntary movements (making a fist, pointing with the arm unrestrained, etc.), and performance of simple behavioral tests. Sensory and motor activity will be assessed by standard techniques including recordings from EMG and EEG electrodes, and accelerometers.

Electrical stimulation of the brain is carried out at 1.5 milli-amp currents to evoke somatic, visual and auditory sensations, and to influence the disordered movements.

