For implanting the ECoG strip, the preoperative MRI study will be used to plan the surgical target and trajectory. We will identify a point on the primary motor cortex (M1), 3 cm from the midline, based on anatomical identification of the central sulcus. The goal is to target the arm-related area of M1, slightly medial to the 'hand knob' (Yousry et al., 1997), in the same parasagittal plane as the typical entry site for placement of the subthalamic nucleus or thalamic deep brain stimulator electrodes. The location on the scalp will have a radio-opaque marker stereotactically placed on it. After drilling the frontal burr holes and opening the dura mater an eight-contact subdural electrocorticography strip (2.3 mm contacts, 1 cm spacing) will be placed on the brain surface and directed posteriorly in a parasagittal plane to provide contacts covering M1 and the primary sensory cortex (S1). In some cases, one subdural strip may be placed through both burr holes. The location of the burr holes will be determined by the selection of the safest entry point for the intended deep brain stimulator trajectory with no additional skull or scalp exposure needed for electrocorticography strip placement. The burr hole will then be sealed with a fibrin sealant after placement of the electrocorticography strip (and guide tube for microelectrode recording/deep brain stimulator lead placement).

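### In the one-stimulus button version of the attention task, the painful stimulus draws a hand movement only when pain is attended, so that version's neural attention contrast estimates attention plus movement

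*Combined protocol and SAP*

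**What the plan says.** Section 2 makes the effect of attention on spike, LFP and EEG activity part of the secondary outcome of Objective I. The tasks are in Section 4, under Objective III: Sensory Processes: Behavioral Tasks. Painful and non-painful stimuli arrive in one random train, and the subject either counts the target or has to "push buttons in response to the painful stimulus (attention to pain), or the non-painful stimulus (distraction from pain) or both", with conditions "as presented in random order and counterbalanced across patients". Three further trains follow: counting non-painful stimuli only, counting painful stimuli only, and receiving painful stimuli while doing a cognitive task such as reading.

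The same section repeats the choice of response for healthy subjects and chronic pain patients, among others: "The subject will be asked to count the stimuli or signal the occurrence of one or both stimuli by key presses". It also says that attention testing is done in the operating room.

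On recording sites, Surgical Standard of Care Procedures states: "The surgical procedures target the Ventral intermediate nucleus of the Thalamus (Vim), the Subthalamic nucleus, and the Globus Pallidus". For the cortical strip it states: "The goal is to target the arm-related area of M1". Under Timeline/Timing of Procedures, extra-operative brain monitoring is EEG only, and EMG and accelerometers are optional.

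Section 3 states: "Activation by sensory stimuli or movements will be determined by examining changes in neuronal firing rates"; it adds EEG frequency and spectral power as further readouts. Section 7 plans descriptive summaries, paired and unpaired comparisons, and connectivity measures. It does not say which response mode supports the attention contrast.

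**The concern.** The attention contrast should compare the brain's response to the same painful stimulus when it is attended and when it is not. In the one-stimulus button version a second thing changes with the instruction: the subject prepares and makes a hand movement to the painful stimulus in one condition and not in the other.

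Objective II expects movement-related activity in cortical and deep nuclei, and Section 3 reads activation by movement from the same signals as activation by sensory stimuli. On the plan's own premises, then, a movement signal should appear in this contrast. If it is read as attention, ordinary motor activity in motor structures would be reported as attentional modulation of pain networks.

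**Working it through.** The plan gives no sample size, effect size or error rate for this task, so there is no figure to reproduce. The check is whether the design can tell attention from movement.

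**Step 1: code the cells** from the response rule in the Behavioral Tasks section (1 = yes, 0 = no).

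| Target | Stimulus | Attended | Press, button version | Press, counting version |
|---|---|---|---|---|
| Painful | painful | 1 | 1 | 0 |
| Painful | non-painful | 0 | 0 | 0 |
| Non-painful | painful | 0 | 0 | 0 |
| Non-painful | non-painful | 1 | 1 | 0 |
| Both | painful | 1 | 1 | 0 |
| Both | non-painful | 1 | 1 | 0 |

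**Step 2: button version alone.** Attended and press are identical in every row, so their correlation is 1.0. A model with an intercept, stimulus type, attended and press has rank 3 with 4 columns. Leaving out the two rows where both stimuli are targets changes neither result.

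**Step 3: the contrast for the painful stimulus.** Let A be the attention effect and M the movement effect.

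- Button version: attended minus distracted = A + M.
- Counting version: attended minus distracted = A.
- Both stimuli as targets: the painful stimulus is always attended and always pressed, so there is no distracted condition within the block. Set against the distraction block, the difference is again A + M.

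**Step 4: both versions in the same analysis.**

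- With the two one-stimulus instructions there are 8 cells: 4 attended, 2 pressed, and every pressed cell is attended. The correlation is (2/8 − 4/8 × 2/8) / √[(4/8 × 4/8)(2/8 × 6/8)] = 0.125/0.217 = 0.58.
- With the instruction to respond to both there are 12 cells, 8 attended and 4 pressed. The correlation is (4/12 − 8/12 × 4/12) / √[(8/12 × 4/12)(4/12 × 8/12)] = (1/9)/(2/9) = 0.50.
- The model has full rank in both cases (4 of 4, or 5 of 5 with a main effect of response mode). A and M are then separable if they add. The plan does not require both versions in the same subject.

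**Step 5: size.** The documents give neither A nor M. The movement share of the apparent effect is M/(A + M). With A set to 1 as an assumption:

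| M | Button contrast | Movement share |
|---|---|---|
| 0 | 1 | 0% |
| 0.5 | 1.5 | 33% |
| 1 | 2 | 50% |
| 2 | 3 | 67% |

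**Step 6: does anything in the plan remove M?** Counterbalancing balances order, but the press is part of the condition. EMG and accelerometers can time the movement, but knowing its time does not break the identity in Step 2. Section 7 specifies no movement-matched contrast, delayed response or analysis window.

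**The case against.** The strongest reply is that the plan already contains contrasts free of the press. Counting is the first response option, and the trains of counted pain and of pain during reading compare attended with distracted pain without a button. This stands. A reader might infer that the whole attention outcome is mixed with movement, or that the study cannot separate the two; the documents do not support either. The problem belongs to one response option analysed alone. Nor does Section 7 say that this version will be the neural attention contrast. What remains is that no rule says who counts and who presses, or that the versions are kept apart.

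Scope is also limited. Deep nuclei and the cortical strip are recorded only during surgery; healthy and chronic pain participants have scalp EEG alone. Their key presses are described as detection responses ("signal the occurrence of one or both stimuli by key presses, which indicate detection of that stimulus"), so the confound applies there only if one-stimulus presses feed an attend-versus-distract comparison.

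Third, M may be small for some measures. Activity well before the press carries less of it, and the plan states neither the responding hand relative to the recorded side nor the window. This stands as a reason not to attach a size. It does not clear late components, ongoing power or connectivity.

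A reader might also infer that patients with bradykinesia or tremor would appear to differ in attention. The documents plan no comparison of attention by motor severity, so that is not claimed.

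Finally, this is a secondary outcome of a study declared exploratory. That limits the consequence to interpretation, since no powered test is affected. It does not make the contrast interpretable.

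**Conclusion.** The point holds for the one-stimulus, immediate-press version of the attention task. There, attending to the painful stimulus and moving to it are perfectly collinear, and the attend-minus-distract neural contrast estimates A + M. This follows from the response rule and needs no assumed effect size. It assumes only that subjects press as instructed; misses and false presses would loosen the identity slightly, but misses are themselves lapses of attention.

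How much M matters cannot be read from the documents; the shares of 0% to 67% above are illustrations for M between zero and twice A. The exposure is greatest in intraoperative recordings from the motor targets and arm-area M1, and smaller but present in scalp EEG over motor cortex. The counting version and the counted-pain versus reading trains are not affected by this confound. The change is inexpensive and worth making.

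**What to change.** In the Behavioral Tasks section, add a rule for both places where the choice of response is given:

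- Neural attention contrasts (spike, LFP, ECoG, EEG) use counting trials, or trials in which the press is delayed past a stated analysis window.
- Attend-versus-distract contrasts from the one-stimulus, immediate-press version are not used for neural outcomes. That version is kept for behaviour: detection and reaction time.

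The instruction to respond to both stimuli should not be offered as a substitute. It equalises the movement but leaves no distraction condition.

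The cost is a wording change. Counting is already in the protocol and needs no new equipment or subjects; a delayed press would need a changed instruction and a stated window. The downside is no trial-by-trial reaction time on counting blocks.
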